7.3 Recall bias

- Similar to both selection and survival bias above, this potential source of bias will be assessed based on evaluations of facility-level data as outlined in section 5.3.1.

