enrolled, a form of systematic measurement error called recall bias may result from an attempt to collect data retrospectively from those with a recent history of COVID-19. However, this potential source of bias will be assessed based on evaluations of facility-level data and stratified assessments of HCWs according to their index date (i.e., duration from the first known exposure to COVID-19 patients to the date of enrollment).

- All information is self-reported, and there is no mechanism to verify the accuracy of information entered into the web-application. Relatedly, the reporting of outcomes of hospitalization and death are dependent on the reliable participation of a secondary contact, who may be difficult to contact in the case of an HCW's death.
- Association of compared therapies may be confounded by non-random treatment selection/allocation that may have its provenance in unknown mechanisms associated with confounding by indication and channeling bias, among others. These may at least, in part, be addressed through the use of causal graphical models in association with appropriate statistical cohort balancing techniques, such as propensity score analysis and matching, and inverse probability weighted estimators, to be detailed in the SAP.
- The study may also be affected by protopathic bias in which the timing of, for example, formal diagnosis with regard to when symptoms and treatment occurs can result in incorrect causal inference regarding the effect of the treatment exposure on the risk of the outcome. A common general example is when patients are prescribed a drug to address disease symptoms ahead of the formal diagnosis of the disease which can lead one to incorrect inference regarding the effect of the treatment. Sensitivity analyses will be conducted among the subgroup of HCWs for which PCR-confirmed absence of infection at index date is demonstrated, and according to the subgroup of HCWs for which serology results are available.
- Since the data for this study are self-reported by HCWs who may not complete all surveys, this could lead to incomplete/missing data. In addition, there are possibilities of errors in recording information or missing information due to technical errors in the website/mobile application. To mitigate this risk, weekly SMS reminders and emails will be sent to HCWs. There is also an option of follow-ups via phone call with HCWs as and when required.

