5 Determination of Sample Size

The targeted sample size of approximately 10,000 HCWs assumes that 20% of the study population are non-exposed to potential prophylactic treatments, with a baseline risk of SARS-CoV-2 infection in the study period of 10% (for unexposed: not treated with potential prophylactic treatment). A total of N=10,000 allows for 80% power to identify an effect size of Relative Risk = 0.78.

If these sample sizes are not reached with respect the study population being exposed/non-exposed to potential prophylactic treatments, the relative risk may be detected with lower power or it may not be statistically significant. However, the secondary objectives can still be examined.

6 Statistical analysis

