6.1 Overview

All statistical analyses will be conducted using R (version 1.3.1093), unless otherwise specified.

For all descriptive analyses, categorical variables will be summarized by number of observations and percentage (%). Percentages will be rounded to one decimal place and will be based on available observations (known values), unless otherwise specified. Continuous variables will be summarized using descriptive statistics (n, mean, with standard deviation; minimum, first quartile, median, third quartile,

and maximum). Outliers will be included in descriptions as part of presenting ranges and percentiles (25th and 75th). The mean and SD will be rounded to one decimal place.

All statistical tests will be two-sided and at 5% level of significance.

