6.3.1 Facility characteristics

Each facility will be descriptively summarized using data from separately completed facility level questionnaires; these questionnaires will be administered twice - at the start and end of the HCW level survey at each facility. This data will then be linked to HCW level data from the same facility to provide a broader context for the survey data, as well as to compare the results from HCW level survey with what could have been expected from the facility level data. Subsequently, an assessment of potential biases and limitations in this regard will be discussed in a study report.

In particular, a description of facilities will be provided in terms of type (public/private/community; teaching status) and size (number of beds), as well as existence of policies for prophylactic treatment and PPE use to prevent COVID-19 among HCWs. In addition, existence of BCG vaccination policy for HCWs and shortage of COVID-19 tests experienced by the facility will be described, as recorded in the facility level survey.

Also, the number of HCWs exposed to COVID-19 patients at each facility, the number of HCWs tested for, diagnosed with and died due to COVID-19 at each facility will be described, both since the start of pandemic (including within the last 30 days) and at the end of the survey in the facility.

The number of patients tested and treated for COVID-19 at each facility will be described too.

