6.6 Subgroup analyses

The adjusted analyses of the primary and secondary outcomes will be replicated:

- According to the subgroup of HCWs by COVID-19 status at entry, i.e. separately for those who already had COVID-19 at entry vs those without COVID-19 at entry
- According to the subgroup of HCWs for which PCR-confirmed absence of infection at index date is demonstrated
- According to the subgroup of HCWs for which serology results are available at entry and follow-up
- According to the time from index date to entry in the registry date. Depending on the distribution of the length of time from index date to study enrollment date in these two times, a subgroup analysis may be undertaken. Groups will be formed by binning time from index date to study enrollment date (eg. 0-1 month, 1-2 months, 2-3 months, greater than 3 months)

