7.2 Survival bias

- To assess the impact of this bias, a metadata of healthcare facility level variables will be collected at time of the registry establishment and at the end of the study, including number of exposed to COVID-19 HCWs, number of HCWs who developed COVID-19 and who died from COVID-19 at each participating healthcare facility. This analysis is outlined in section 5.3.1.

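### SAP 7.3 relies on facility totals that cannot show differential recall and omits the protocol's stratification by time from index date to enrolment; for survival bias (SAP 7.2) the totals bound the bias but do not show which exposure group the missed cases came from.

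*SAP*

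**What the plan says.** SAP 7.3 gives recall bias a single assessment: "this potential source of bias will be assessed based on evaluations of facility-level data as outlined in section 5.3.1". The cross-reference is stale, and the facility section is now 6.3.1. SAP 7.2 uses the same source for survival bias: "To assess the impact of this bias, a metadata of healthcare facility level variables will be collected at time of the registry establishment".

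SAP 6.3.1 and Protocol Table 2 list what is collected from each facility: type, beds, patients tested and treated, policies, test shortages, and HCW counts. Of the HCW counts, SAP 6.3.1 says "the number of HCWs tested for, diagnosed with and died due to COVID-19 at each facility will be described". No count is divided by prophylaxis use. The only prophylaxis item is whether the facility has a policy. SAP 6.3.1 plans to link these data to the HCW records and to compare observed with expected results.

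Protocol 8.9 describes recall bias as arising when data are collected retrospectively from HCWs with recent COVID-19. It pairs the facility data with "stratified assessments of HCWs according to their index date", meaning the interval from first known exposure to enrolment. Protocol 8.7.6 lists a replication of the adjusted primary analysis by that interval, without condition. SAP 6.6 keeps the item but, depending on how the intervals are distributed, says only that "a subgroup analysis may be undertaken". The same SAP list firmly plans a replication by COVID-19 status at entry.

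**The concern.** HCWs may enrol after infection, and in SAP 6.4.1 the clock for untreated HCWs starts at first known exposure, which can precede enrolment. Part of the exposure history behind the primary hazard ratio is therefore recalled, by some people who already know that they were infected. SAP 7.4 adds that self-reports cannot be verified.

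If cases and non-cases recall prophylaxis differently, cases are misfiled between treated and untreated. That moves the hazard ratio and leaves the number of cases at each facility as it was. A check based on facility totals cannot register the change.

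Survival bias differs in degree. Cases who never enrol do lower the registry's total against the facility's, so a shortfall is visible. Protocol 8.9, however, is concerned with error in the estimated risk by prophylaxis use, and an unsplit total does not say whether treated or untreated cases are missing.

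**Working it through.** **1. The plan's own figure.** Inputs from SAP section 5 and 6.1: "A total of N=10,000 allows for 80% power to identify an effect size of Relative Risk = 0.78"; the plan "assumes that 20% of the study population are non-exposed to potential prophylactic treatments"; untreated risk 10%; "All statistical tests will be two-sided and at 5% level of significance".

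- Untreated: 2,000 × 0.10 = 200 cases. Treated: 8,000 × 0.078 = 624 cases. Total 824.
- Schoenfeld power = Φ(√(824 × 0.2 × 0.8) × |ln 0.78| − 1.96) = Φ(11.48 × 0.2485 − 1.96) = Φ(0.893) = 81%.

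This agrees with the stated 80%. The figure is not in dispute; it supplies the counts used below.

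**2. Recall bias.** Assume an inert drug: 800 cases among 8,000 treated and 200 among 2,000 untreated. A fraction f of treated cases fails to report prophylaxis, and everyone else reports correctly. With m = 800f,

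RR = [(800 − m)/(8,000 − m)] ÷ [(200 + m)/(2,000 + m)].

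| f | m | Total cases | Observed RR |
|---|---|---|---|
| 0% | 0 | 1,000 | 1.00 |
| 2% | 16 | 1,000 | 0.92 |
| 4% | 32 | 1,000 | 0.84 |
| 6% | 48 | 1,000 | 0.78 |
| 10% | 80 | 1,000 | 0.68 |

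At 6%: (752/7,952) ÷ (248/2,048) = 0.0946 ÷ 0.1211 = 0.78. Error in the other direction does the reverse: if 10% of untreated cases (20) wrongly report prophylaxis, the RR is (820/8,020) ÷ (180/1,980) = 1.12. In every row the registry and facility totals agree exactly.

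**3. Survival bias.** Use the design's 824 cases and true HR 0.78. Let c_T and c_U be the proportions of treated and untreated cases that the registry captures. Simple ratio, denominators held fixed: observed HR = 0.78 × c_T/c_U.

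Extremes for a given overall capture:

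- 98% captured: 0.02 × 824 = 16.5 missed. All treated: 0.78 × 607.5/624 = 0.76. All untreated: 0.78 × 200/183.5 = 0.85.
- 95% captured: 41.2 missed. All treated: 0.78 × 582.8/624 = 0.73. All untreated: 0.78 × 200/158.8 = 0.98.

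At an assumed 80% capture (0.8 × 824 = 659.2), c_U = (659.2 − 624c_T)/200:

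- c_T = 75% gives c_U = 96% and HR 0.78 × 0.75/0.956 = 0.61.
- c_T = 90% gives c_U = 49% and HR 0.78 × 0.90/0.488 = 1.44.

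Removing the missed cases from the denominators as well changes these to 0.62 and 1.38. One facility total therefore fits apparent benefit and apparent harm.

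**4. Protocol against SAP on recall.** Protocol 8.9 has facility data plus stratification by interval; Protocol 8.7.6 states the interval analysis without condition. SAP 7.3 has facility data only; SAP 6.6 has the interval analysis under a condition. The SAP says that it follows protocol version 1.0. The amendment log lists no change to 8.7.6 and, in 8.9, only an added paragraph on missing data, so the version gap does not appear to explain the difference.

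**The case against.** The strongest reply is that the plan does more about recall than SAP 7.3 says. SAP 6.6 firmly replicates the adjusted analyses by COVID-19 status at entry. The stratum without COVID-19 at entry removes most retrospectively reported cases, which is where Protocol 8.9 locates the problem. That stands, so a reader who inferred from SAP 7.3 that recall bias is left to facility totals alone would be wrong. Three gaps remain. SAP 7.3 does not cite the subgroup; SAP 6.3.5 uses it for the dating of medical history. In the stratum with COVID-19 at entry everyone is a case, so it has no non-cases against which to measure infection risk, and contrasting the two strata is not a clean recall test. In the other stratum, a weekly report may still be completed after the infection in that week.

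A second reply concerns survival bias. A reader might infer that agreement between facility and registry totals says nothing about the hazard ratio. The arithmetic does not support that: at 98% capture the bias is confined to a narrow range. The plan also has secondary contacts, a description of loss to follow-up by prophylaxis use (Protocol 8.9) and an analysis counting drop-outs as events (SAP 6.7). These address losses after enrolment, not HCWs who never enrolled. Facility policy status allows a crude contrast between facilities, but policy is not individual use.

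Nor do the documents say that matching totals would be presented as validating the hazard ratio. SAP 6.3.1 offers them as context, with biases and limitations to be discussed.

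**Conclusion.** The point holds in a limited form. The check named in SAP 7.3 cannot show differential recall, and the SAP weakens the HCW-level analysis that the protocol set beside it. The stakes are material: under the assumptions in step 2, misreporting by 48 of 800 treated cases turns no effect into the design effect of 0.78 with no trace in the totals. For survival bias, facility totals are informative about how many cases are missing. They bound the hazard ratio tightly if capture is near complete (0.76 to 0.85 at 98%) and loosely if it is not (about 0.61 and about 1.4 both fit 80%), and they never identify the group.

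The misreporting and capture rates are assumptions; the documents give none. The calculations treat the HR as a risk ratio and assume that all non-cases are enrolled. They show what the checks can and cannot detect and do not predict the bias in this registry. The SAP should be changed, but the point does not by itself invalidate the primary analysis.

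**What to change.** 1. **SAP 6.6 and 7.3.** Make the analysis by time from index date to entry unconditional, as in Protocol 8.7.6. In 7.3, cite it and the subgroup without COVID-19 at entry as the recall-bias assessment, and correct the section number.
2. **SAP 6.7.** Add a rerun of the primary model restricted to person-time from enrolment, using only prophylaxis, PPE and contact reported in a survey completed before the infection date. Report its hazard ratio beside the primary one.
3. **SAP 7.2.** State that facility totals show overall under-capture only. Take the number of missed cases from them, and report the range of the hazard ratio over stated splits of those cases between treated and untreated HCWs.

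The cost is SAP wording, the additional runs and a short bias calculation. The restricted analyses will have fewer events and wider intervals, so a difference from the primary estimate needs cautious reading. No new data are required.

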7.4 Information bias

- All information is self-reported, and there is no mechanism to verify the accuracy of information entered into the web-application. Relatedly, the reporting of hospitalization and death are dependent on the reliable participation of a secondary contact, who may be difficult to contact in the case of an HCW's death.

7.5 Indication bias

- Association of compared therapies may be confounded by non-random treatment selection/allocation that may have its provenance in unknown mechanisms associated with confounding by indication and channeling bias, among others. These may at least, in part, be addressed through the use of inverse probability weighting as outlined in section 5.4.2 by adjusting for relevant covariates (ie. confounders).

7.6 Protopathic bias

- The study may also be affected by protopathic bias in which the timing of, for example, formal diagnosis with regard to when symptoms and treatment occurs can result in incorrect causal inference regarding the effect of the treatment exposure on the risk of the outcome. To assess the impact of this bias, as outlined in section 5.6, sensitivity analyses will be conducted among the subgroup of HCWs for which PCR-confirmed absence of infection at index date is demonstrated, and according to the subgroup of HCWs for which serology results are available.

8 References

1. COVID-19 Therapeutic Trial Synopsis. https://www.who.int/blueprint/prioritydiseases/key-action/COVID19_Treatment_Trial_Design_Master_ProtocolSynopsis_Final_18022020.pdf?ua=1. Last accessed on 23Apr 2020.
2. Risk assessment and management of exposure of health care workers in the context of COVID-19. WHO Interim Guidance, 19 Mar 2020. https://apps.who.int/iris/bitstream/handle/10665/331496/WHO-2019-nCovHCW_risk_assessment-2020.2-eng.pdf. Last accessed on 14 Apr 2020.
3. Austin, Peter. (2017). A Tutorial on Multilevel Survival Analysis: Methods, Models and Applications: Multilevel Survival Analysis. International Statistical Review. 85. 10.1111/insr.12214.
4. Grafféo, Nathalie & Latouche, Aurélien & Le Tourneau, Christophe & Chevret, Sylvie. (2019). ipcwswitch: An R package for inverse probability of censoring weighting with an application to switches in clinical trials. Computers in Biology and Medicine. 111. 103339. 10.1016/j.combiomed.2019.103339.

9 Appendix

WHO Ordinal Scale for Clinical Improvement¹

Patient State	Descriptor	Score
Uninfected	No clinical or virological evidence of infection	0
Ambulatory	No limitation of activities	1
	Limitation of activities	2
Hospitalized Mild disease	Hospitalized, no oxygen therapy	3
	Oxygen by mask or nasal prongs	4
Hospitalized Severe Disease	Non-invasive ventilation or high-flow oxygen	5
	Intubation and mechanical ventilation	6
	Ventilation + additional organ support – pressors, RRT, ECMO	7
Dead	Death	8

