3.1 Study design

The UNITY Global Registry is designed to collect data on healthcare workers exposed to SARS-CoV-2 using longitudinal serial surveys implemented through a web/mobile application-based technology to encourage participation and facilitate rapid responses during this pandemic. Countries and healthcare facilities were selected based on the availability of potential prophylactic treatments to prevent workplace infection from SARS-CoV-2. Individuals with workplace exposure to confirmed or clinically diagnosed COVID-19 patients prior to enrollment, or anticipated within 30 days after enrollment, are eligible to participate. COVID-19 exposure is defined as per WHO classification¹. The date of the HCW's first known exposure to a confirmed or clinically diagnosed case of COVID-19 is referred to as the "Index Date" (see Figure 1). Healthcare worker volunteers are ineligible if they had COVID-19 or symptoms highly suggestive of COVID-19 before the Index Date. However, at the time of enrollment, HCWs can be either SARS-CoV-2 positive (symptomatic or asymptomatic) or SARS-CoV-2 negative. Healthcare workers are identified for participation via a central contact at participating healthcare facilities and are directed to a website/mobile application allowing them to electronically consent and answer questions that help assess their eligibility to participate. Information on potential prophylactic treatments used by HCWs are also collected.

All eligible HCWs in the study facilities are asked to enter the data in the registry via electronic data collection form. Data is collected at entry to the registry, and then weekly until 12 weeks after enrollment, death or lost to follow-up, whichever is earlier. A secondary contact is identified to be contacted to confirm status of HCWs in case of non-response/ loss to follow-up. In case of conflicts, responses by HCWs take precedence. Serology results from the laboratory will be loaded into the Local Data Store and merged with HCW contact information based on the participant identification numbers. Notification of results may be made available to the HCWs via secure access.

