This is an observational cohort study; therefore, no preventive interventions, visits or laboratory tests are mandated. Dosing and duration of potential prophylactic treatment is at the discretion of the institution and/or healthcare provider, in accordance with regular local practice. However, serology testing for SARS-CoV-2 antibodies are being offered to the first 50% of participating HCWs per country, at enrollment and at the last follow-up (i.e. at Week 12).

Figure 1: Healthcare Worker Flow – Study Schematic

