6.4 Primary analysis

6.4.1 Frailty model: mixed effect Cox regression

For the time to COVID-19 infection outcome, both crude and adjusted hazards ratios will be estimated for time to COVID-19 infection with respect to prophylaxis use. The primary objective of this analysis is to assess the association between prophylactic treatments and the reduced risk of SARS-CoV-2 infection in HCWs caring for COVID-19 patients. A mixed effect Cox regression model (ie. frailty model) will be used to estimate adjusted hazard ratios. This method will allow the utilization of both the repeated measures gathered from each HCWs surveys, as well as the incorporation of time-varying covariates of interest such as PPE usage and COVID-19 exposure. Each subject will be included as a random effect. Both time-fixed and time-varying covariates will be included in the model. Covariates will be assessed using a univariate model, any covariates with a p-value less than 0.20 will be included in a multivariate model. A backward stepwise process will then be completed, where the covariates with largest p-value are removed one at a time until all covariates that remain are significant at the 0.10 level. The time-fixed covariates, healthcare facility and country will be included in the model regardless of their significance level. Including the healthcare facility and country covariates will make each healthcare worker's COVID-19 outcome conditionally independent on the background COVID-19 incidence occurring within each subject's healthcare facility and country. A list of additional covariates to be considered can be found in Table 5.4.1. For each subject in the control group, the index date (ie. time of first known exposure to COVID-19 patients) will be used as time zero. For HCWs that are treated with prophylaxis at any time their index date will be 7 days after initiation of treatment. Having an index date near treatment initiation will prevent the introduction of survivorship bias into the analysis.

Table 5.4.1 Model Covariates

Time-fixed/Time-varying Covariate	Covariate Name
Time-fixed Covariates	Healthcare facility, Country, Age, Biological Gender, BMI, Smoking status, Ethnicity, Blood type, Primary work location, Type of healthcare worker, Medical history

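### The PCR-negative subgroup used to check protopathic bias is tied to an index date that the SAP defines in two ways, neither of which is the date the drug was started

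*SAP*

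**What the plan says.** - SAP 7.6 offers two checks for protopathic bias. The first is that "sensitivity analyses will be conducted among the subgroup of HCWs for which PCR-confirmed absence of infection at index date is demonstrated". The second is the subgroup with serology results. It points to a section 5.6 for both; in the SAP's present numbering the subgroup list is 6.6.
- SAP 6.6 words the first check as "According to the subgroup of HCWs for which PCR-confirmed absence of infection at index date is demonstrated". Protocol 8.7.6 has the same item among its sensitivity analyses.
- SAP 3.1 ties the term to exposure: the date of the HCW's "first known exposure to a confirmed or clinically diagnosed case of COVID-19 is referred to as the" index date. SAP 3.3 and Protocol 8.1 use it in the same sense.
- SAP 6.4.1 keeps first exposure as time zero for controls but adds a second meaning: "For HCWs that are treated with prophylaxis at any time their index date will be 7 days after initiation of treatment".
- On testing, SAP 3.1 states that "no preventive interventions, visits or laboratory tests are mandated". No window is given for how close to the index date the negative PCR must lie.

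**The concern.** Protocol 8.9 gives the mechanism: a drug is taken for symptoms before the disease causing them has been formally diagnosed. SAP 7.6 is less specific and speaks only of the timing of diagnosis relative to symptoms and treatment. On either wording, what matters is whether the HCW was already infected when the drug was started. A negative PCR at another date does not answer that.

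This is one of only two checks named for this bias. If the subgroup keeps the HCWs who create the bias, its estimate can agree with the primary one, and the agreement is likely to be reported as evidence that the bias is absent.

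**Working it through.** The plan attaches no figure to this check, so the working sets the sections side by side.

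**1. Which index date applies?** SAP 6.6 and 7.6 do not say. First exposure is the likelier meaning for two reasons. The subgroup wording comes from Protocol 8.7.6, and the protocol has no other index date. The last item in the SAP 6.6 list also fits only that meaning comfortably: "Groups will be formed by binning time from index date to study enrollment date", with example bins running to more than three months.

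**2. First-exposure meaning.** Take an HCW with this order of events: first exposure with a negative PCR, later infection, early symptoms, drug start, formal diagnosis. The HCW meets the subgroup definition and stays in. Such starts are expected: SAP 6.3 compares rates by pre- and post-exposure use, and SAP 6.3.7 describes use before and after first exposure. The example bins in 6.6 show that the index date can lie months before enrollment, so the gap between index date and drug start may be long. For an HCW who started the drug before first exposure, the index-date test comes after drug start and this gap does not arise in the same way.

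**3. Drug start plus seven days.** Here the treated HCW's test is tied to treatment, but to a point one week into it. It is still not a test of status at drug start.

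**4. Do the other safeguards test status at drug start?**

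| Safeguard | Where | Anchor |
|---|---|---|
| Exclusion for prior infection | SAP 3.1.1.2 | First exposure |
| Split by COVID-19 status | SAP 6.6 | Registry entry |
| Serology subgroup | SAP 6.6, 7.6 | Entry and follow-up; Protocol Table 1 allows the baseline sample up to Week 8 |
| Drug use before infection, HCWs infected at entry | SAP 6.3.7 | Infection date, but descriptive only |

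None does so in an adjusted analysis.

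**5. Does the seven-day shift of time zero close the gap?** Only in part. SAP 6.4.1 does not say what happens to an infection or symptom dated before a treated HCW's time zero. Three treatments are open:
- A diagnosis dated after day 7 is counted as a treated event, which pushes the hazard ratio up.
- The HCW is dropped, and an event that arose while untreated is lost.
- The HCW is kept as event-free treated follow-up, which pushes the hazard ratio down.

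The direction of any remaining bias is therefore not fixed by the plan.

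**6. Size.** A magnitude would need the share of HCWs with a PCR near the index date, the distribution of time from index date to drug start, and the share of starts prompted by symptoms. The documents give none of these.

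**The case against.** The strongest defence is that the plan already blunts the problem. With time zero seven days after drug start, a diagnosis made at or within a week of starting falls before the treated HCW's follow-up begins, and those are the typical protopathic events. The primary outcome in SAP 3.5.1 also counts infection by symptoms, and onset dates are collected, so a symptomatic starter may already have an event dated before drug start. SAP 6.6 splits HCWs by status at entry as well. This stands as partial protection. It is not full protection, because the handling of events before time zero is unstated and SAP 6.3.9 leaves the qualifying symptoms to be settled after the descriptive analysis.

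It is also fair that the gap in the first-exposure reading concerns only HCWs who start after first exposure.

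A reader might infer something stronger from the second index date: that requiring a negative PCR a week into treatment strips early infections from treated HCWs only and so favours the drug, by about one-twelfth of 12-week events. The documents do not support this. With time zero at drug start plus seven days, a Cox model already leaves earlier infections out of the treated risk set, so any asymmetry comes from 6.4.1 and not from the subgroup. The 10% risk behind that fraction is stated in SAP 5 for untreated HCWs only.

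**Conclusion.** The point holds in a limited form. The PCR check for protopathic bias has an ambiguous anchor, and neither candidate is drug start. Under the likelier first-exposure meaning, it cannot remove HCWs who started a drug after exposure because of early symptoms, so agreement with the primary result would not show that the bias is absent.

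This rests on two things: that 6.6 and 7.6 use the first-exposure meaning, which is probable but not stated, and that some HCWs start a drug after exposure, which SAP 6.3 expects. No numerical size or direction can be derived. Nor do the documents show how small the PCR subgroup will be; they show only that testing is not mandated and that no window is set. It should be corrected before analysis, since the better check uses dates already collected.

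**What to change.** 1. **Add a date-ordering rerun to SAP 6.6 and 7.6.** Repeat the primary analysis so that a drug start dated on or after the HCW's first COVID-19 symptom onset, diagnosis or positive test does not count as exposure. That HCW keeps the first-exposure time zero and the event is counted as untreated. Do a second run that excludes such HCWs.
2. **Redefine the PCR subgroup.** Require, for treated HCWs, a last negative PCR in a stated window on or before drug start. For controls, require it in the same window on or before a comparable matched date, placed so that the interval from test window to time zero is the same in both groups. Allow no symptoms or positive test in between. Report how many HCWs qualify in each group.
3. **State the handling of events before time zero** for treated HCWs in 6.4.1, name the anchor date in 6.6 and 7.6, and correct the cross-reference in 7.6.

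**Cost.** SAP wording and a few reruns. Drug start dates (SAP 3.6.2) and symptom and test dates (SAP 3.6.5) are already collected. The PCR subgroup may be small, so the rerun in item 1 is likely to carry most of the weight. That rerun depends on self-reported dates and on the symptom definition the SAP still has to fix. SAP 6.2.1 fills in partial dates, so the report should say how many HCWs have an order of events that rests on an imputed date.
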